### 6.5 CONCOMITANT THERAPY

Participants in the study may be receiving ongoing treatment for their chronic pain, as listed in the table below.

Category	Specific therapy
Procedures	Injections (steroid, facet joints, radio frequency ablations, sacroiliac joint injections, Epidural injections, inter laminar or transforaminal)
	TENS unit

	Blocks (facet blocks, medial branch blocks, trigger point injections)
	Acupuncture
Physical Therapy	Physical Therapy and Aqua therapy
	Chiropractic care
Psychotherapy	CBT
	Biofeedback
	Screening and management of depression/anxiety
Medications	Benzodiazepine tapering program
	Opioid maintenance and tapering program
	Tylenol
	Muscle Relaxants
	Narcotics
	Gabapentin/pregabalin
	NSAIDS
	Cannabinoids

#### 6.5.1 RESCUE MEDICINE

NA

### 7 STUDY INTERVENTION DISCONTINUATION AND PARTICIPANT DISCONTINUATION/WITHDRAWAL

#### 7.1 DISCONTINUATION OF STUDY INTERVENTION

We do not anticipate any events that would cause the study intervention to be discontinued.

#### 7.2 PARTICIPANT DISCONTINUATION/WITHDRAWAL FROM THE STUDY

Participants are free to withdraw from the study at any time upon request. Participants request to withdraw will be asked to clarify whether they wish to discontinue the intervention but still complete the periodic survey questionnaires. In this case, the participant would not be considered withdrawn.

An investigator may withdraw a participant who develops any of the exclusions criteria in section 5. The reason for participant discontinuation or withdrawal from the study will be recorded.

Subjects who signed the informed consent form, were randomized and received the study intervention, and subsequently withdraw, or are withdrawn or discontinued from the study without engaging with the VR intervention will be replaced. Participants are considered to have engaged with the VR intervention if there is any self-reported VR usage in survey questionnaires or if any metadata are recorded in a participant's headset during their possession of the VR headset.

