## 5.2 EXCLUSION CRITERIA

An individual who meets any of the following criteria will be excluded from participation in this study:

1. Presents with a condition that interferes with VR usage, including history of seizure, facial injury precluding safe placement of headset, significant visual or hearing impairment that impacts ability to see the VR images or follow audio instructions
2. Are being recommended for long-term hospitalization that would require more than three-week stay in the hospital
3. Received surgical procedure within the previous 8 weeks
4. Surgery is planned within the next 3 months
5. Is currently using a spinal cord stimulator
6. Has LBP attributable to a recognizable, specific pathology, including spinal infection, cancer, fracture, or inflammatory spondylopathies, consistent with the NIH Task force on Research Standards for cLBP
7. Previously participated in a VR clinical trial

Women who are currently pregnant or planning to become pregnant will not be excluded from the study

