### 9.3 POPULATIONS FOR ANALYSES

All efficacy and safety data summaries and analyses will be performed by study arm using an Intent-to-Treat (ITT) population defined as all randomized patients.

The number of patients identified as candidates will be reported, as will the number screened (i.e. consented). The number and percentage of patients randomized, patient population (ITT), and treatment status (completed, discontinued/withdrew) will be summarized both by treatment group and overall. Reasons for discontinuation/withdrawal will be presented.

An exploratory, per protocol (PP) analysis will focus on patients who use the assigned intervention on at least 50% of days during the first 30-day period. Usage meta-data on the headsets will facilitate sample definition in this population. If headset meta-data is not available, we will rely on weekly self-report usage surveys.

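### Protocol 7.2 lets an investigator withdraw from the study a participant who develops an exclusion criterion, and nothing keeps that participant's surveys going, so some possibly outcome-related data can be lost needlessly

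*Protocol*

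**What the plan says.** Protocol 7.2, headed "PARTICIPANT DISCONTINUATION/WITHDRAWAL FROM THE STUDY", treats two situations in turn.

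- **The participant asks to leave.** Such a participant "will be asked to clarify whether they wish to discontinue the intervention but still complete the periodic survey questionnaires". For those who do, the protocol adds: "In this case, the participant would not be considered withdrawn".
- **The investigator decides.** "An investigator may withdraw a participant who develops any of the exclusions criteria in section 5". The reason is recorded. Nothing is said about surveys afterwards.

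The criteria in Protocol 5.2 include "Surgery is planned within the next 3 months", "Is currently using a spinal cord stimulator" and "Are being recommended for long-term hospitalization that would require more than three-week stay in the hospital". They also include surgery in the previous 8 weeks, a specific cause for the back pain, and conditions that prevent headset use, such as seizure or facial injury.

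Protocol 9.3 analyses efficacy "using an Intent-to-Treat (ITT) population defined as all randomized patients". SAP 4.6.1 fits an MMRM to PROMIS Pain Interference at Days 7, 15, 21 and 30. Under SAP 6.1, a participant who stops early contributes data up to the last day on which any were given, and MMRM analyses are not imputed by default. SAP 6.4 brings in multiple imputation, under missing at random, only if more than 15% of a key endpoint is missing in a treatment group and the data are not missing completely at random. It mentions looking for non-ignorable missingness but names no model for it.

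**The concern.** At entry, the exclusion criteria define who is eligible. After randomisation, some of them can be consequences of how the back pain has gone. A stimulator or a newly planned back operation is more likely in someone doing badly. If the investigator then ends study participation, the remaining surveys go missing because of an event related to the outcome.

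An MMRM is unbiased when missingness depends only on scores and covariates already in the model. A new surgical plan may carry information that the Day 7-21 scores do not. Any excess deficit among those withdrawn is then unseen, and the arm comparison shifts if the withdrawal rates or the deficits differ between arms.

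The loss is also avoidable. The patient-reported outcomes are electronic questionnaires answered remotely, and a stimulator or an operation does not in itself prevent anyone from answering them.

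**Working it through.** **1. Does any text keep these participants in follow-up?**

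| Place | What it provides | Covers investigator withdrawal? |
|---|---|---|
| Protocol 7.1 | Expects no reason to stop the intervention | No |
| Protocol 7.2, participant request | Stop VR, keep surveys, not counted as withdrawn | No |
| Protocol 7.2, investigator decision | Withdrawal from the study | Silent on surveys |
| Protocol 7.3 | Loss to follow-up through non-response | No |
| Protocol 9.3, SAP 6.1 and 6.4 | Population and handling of missing data | Does not restore uncollected scores |

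By 7.2's own usage, someone who keeps answering surveys is not withdrawn. The natural reading is that someone who is withdrawn stops answering them.

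**2. What is lost, and when?**

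- Withdrawal before Day 30: the primary score and all later surveys.
- Withdrawal after Day 30: later surveys only, such as Day 60 or Day 90.
- Not lost: scores already given. Opioid dose need not be lost, because Protocol 8.1 takes it from the health record and may supplement it from a state database queried for every randomised participant.

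**3. The plan's own power figure.** Inputs from Protocol 9.2: SD 10 at each time and correlation 0, so SD of change = sqrt(100 + 100) = 14.14; 120 per arm; both VR arms 5 points from sham; each compared with sham at two-sided 0.025; success if either is significant. Simulating 100,000 trials gives 83.3%, against 83% stated.

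**4. Precision.** The target of 360 equals 3 x 120, so there is no dropout allowance. The loss rates below are assumed and equal in all arms, using only participants with a Day 30 score.

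| Day 30 scores lost | n per arm | Power, either arm |
|---|---|---|
| 0% | 120 | 83.3% |
| 5% | 114 | 81.3% |
| 10% | 108 | 78.9% |
| 15% | 102 | 76.6% |

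**5. Bias.** Let p be the share of an arm withdrawn before Day 30. Let D be how much worse those participants would have scored than those retained, beyond what the model recovers from earlier scores. A higher score is worse. The full arm mean is the retained mean + p x D, so

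bias in (VR - sham) = p_sham x D_sham - p_VR x D_VR.

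The documents give neither p nor D. Assumed ranges are p from 2% to 10% (2.4 to 12 of 120) and D from 5 points (the target difference) to 10 points (one SD of the scale).

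| p_sham | p_VR | D (both arms) | Bias in points |
|---|---|---|---|
| 5% | 5% | 10 | 0 |
| 5% | 2% | 10 | (0.05 - 0.02) x 10 = +0.3 |
| 2% | 5% | 10 | -0.3 |
| 10% | 5% | 10 | +0.5 |
| 10% | 2% | 10 | +0.8 |
| 2% | 10% | 10 | -0.8 |

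If D also differs by arm, the extreme is 0.10 x 10 - 0.02 x 5 = 0.9 in absolute value. A positive value shrinks a true difference of -5 (to -4.2 at +0.8) and works against VR. A negative value enlarges it and favours VR.

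**6. Would the SAP's safeguard act?** The threshold is 0.15 x 120 = 18 missing per arm. Withdrawals of 2.4 to 12 per arm would not reach it alone. If other losses carried the total past it, the imputation would still assume missing at random.

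**The case against.** The case against is substantial, and most of it limits the point rather than removing it.

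- **A reader might infer that worsening pain costs a participant both Day 30 and Day 90.** The text does not say so. The rule is discretionary, its trigger is an exclusion criterion rather than pain, and only surveys after withdrawal are affected.
- **A reader might infer a contradiction with intention to treat.** There is none. A withdrawn participant stays in the analysis population and contributes the scores already given. The weakness is missing later scores.
- **A reader might infer that 7.2 contradicts itself.** It does not. Participant requests and investigator decisions are different cases, and the second is silent on surveys.
- **A reader might take all the criteria as signs of failing back pain.** Many are not. Surgery and hospitalisation are not limited to the back; infection, cancer or fracture is another diagnosis; seizure and facial injury concern headset use.
- **A reader might infer that the bias must hide a VR benefit.** The documents do not establish which arm would lose more participants. Equal rates and equal deficits leave the comparison unbiased.
- **Few cases are likely before Day 30**, since people with surgery already planned within 3 months are excluded at entry. That is a fair reason to expect the primary analysis to be little affected. It helps less at Day 60 and Day 90.

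What remains is that no provision continues surveys after an investigator withdrawal, and the planned analysis cannot recover what those surveys would have shown.

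**Conclusion.** The point holds in limited form. Following 7.2 as written can create avoidable missing survey data, and for some criteria the missingness can depend on the outcome. No section of either document prevents this. The primary MMRM and the conditional imputation both rest on missing at random, and no alternative model is specified.

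The likely size is modest: under 1 point against a 5-point target, in either direction, with power falling from 83.3% to between 81.3% and 76.6% if 5-15% of Day 30 scores were lost from all causes. These figures rest on assumed rates and deficits. The bias range treats every such withdrawal as falling before Day 30, which probably overstates the primary-endpoint effect. The case for acting rests on the low cost of preventing the loss, not on a large expected bias.

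**What to change.** Amend Protocol 7.2 as follows.

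- Developing an exclusion criterion after randomisation is not by itself a reason to end data collection.
- The existing option to keep completing surveys extends to these participants unless they withdraw consent for it.
- The criterion met and the date of the event are recorded.
- Their observed scores enter the intention-to-treat analysis, and the SAP says so.

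Any decision about headset use stays with the investigators as a separate matter. Removing the investigator's discretion altogether would be broader than the problem requires.

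The cost is a few sentences, since the surveys already run in REDCap. The downside is that some scores will reflect surgery or another procedure. That is partly so already, because Protocol 6.5 permits injections and blocks.

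Timing limits the benefit. Protocol 8.1 planned the last randomisation for 5 September 2023, and Protocol 4.4 ends the study at most 96 days after the last enrolment, which would be about 10 December 2023 if that date held. An amendment helps only those still being followed. For withdrawals already made, the recorded reasons allow the SAP to tabulate them by arm, criterion and study day. A delta-adjusted sensitivity analysis, with the range of D stated before unblinding, would then show whether they matter.

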### 7.3 LOST TO FOLLOW-UP

A participant will be considered lost to follow-up if he or she fails to schedule an onboarding phone call within 30 days of device delivery or if he or she fails to complete the initial SSQ+ survey within 30 days of onboarding completion. For participants who complete the initial SSQ+ survey, fail to complete >80% of future surveys, and become unreachable by phone or email, the participant will be considered lost to follow-up 6 days following the email date of the participant's Day 90 survey.

If a participant fails to complete the Day 90 survey within six days, the following actions will be taken:

- The research coordinator will attempt to contact the participant and counsel them on the importance of completing surveys and returning the equipment to be eligible for the gift card.
- Before a participant is deemed lost to follow-up, the investigator or designee will make every effort to regain contact with the participant (where possible, 3 telephone calls and, if necessary, a certified letter to the participant's last known mailing address or local equivalent methods). Contact attempts will be documented in the participant's study record.
- Should the participant continue to be unreachable, he or she will be considered to have withdrawn from the study with a primary reason of lost to follow-up.

## 8 STUDY ASSESSMENTS AND PROCEDURES

### 8.1 EFFICACY ASSESSMENTS

We will capture all survey data via REDCap. REDCap is a secure web application for building and managing online surveys and databases. While REDCap can be used to collect virtually any type of data (including 21 CFR Part 11, FISMA, and HIPAA-compliant environments), it is specifically geared to support online or offline data capture for research studies and operations. If subjects do not complete the surveys, they will be sent a reminder prompt.

#### *Primary Outcome*

The change from study baseline to Day 30 in pain interference as measured by the 8-item PROMIS Pain Interference scale is the primary endpoint. The scale is rendered using a T-statistic, where a score of 50 represents the population mean and 10 points is a standard deviation (SD). Scoring of the instrument will occur in a SAS/STATA environment in which study statisticians are blinded to the study arm.

#### *Secondary Outcomes*

The change from study baseline to day 90 in pain interference as measured by the 8-item PROMIS PI scale is a secondary endpoint. The scale is rendered using a T-statistic, where a score of 50 represents the population mean and 10 points is a standard deviation (SD). Scoring of the instrument will occur in a SAS/STATA environment in which study statisticians are blinded to the study arm.

The change from study baseline to Day 90 in pain catastrophizing as measured by PCS SF-6 is a secondary endpoint. The Pain Catastrophizing scale (PCS) short form measures rates of high catastrophizing as defined by a score of  $\geq 7$ . Scoring of the instrument will occur in a SAS/STATA environment in which study statisticians are blinded to the study arm.

The change from study baseline to Day 90 in anxiety as measured by the 6-item PROMIS Anxiety scale is a secondary endpoint. The scale is rendered using a T-statistic, where a score of 50 represents the population mean and 10 points is a standard deviation (SD). Scoring of the instrument will occur in a SAS/STATA environment in which study statisticians are blinded to the study arm.

The change from study baseline to day 90 in sleep disturbance as measured by the 6-item PROMIS Sleep Disturbance scale is a secondary endpoint. The scale is rendered using a T-statistic, where a score of 50 represents the population mean and 10 points is a standard deviation (SD). Scoring of the instrument will occur in a SAS/STATA environment in which study statisticians are blinded to the study arm.

The change from study baseline to Day 90 in 7-day average of daily maximum milligrams morphine equivalent (MME) is a secondary endpoint. Prescription data will be extracted from the EHR at baseline and again at Day 90 and may be supplemented by data from CURES. While daily MME of prescriptions is a calculated field in the EHR, calculation of the 7-day average will occur in a SAS/STATA environment in which study statisticians are blinded to the study arm.

CURES is the California Controlled Substance Utilization Review and Evaluation System, a database of Schedule II, III and IV controlled substance prescriptions dispensed in California. It is administered by the California Department of Justice (CA DOJ). We will request prescription data from the CURES database for each randomized patient from 90 days before enrollment until 90 days after the completion of the study. This will allow us to assess prescription changes that might be made right before or after the study ends. The data from CURES will only be used for research purposes and will comply with all requirements of the California Confidentiality of Medical Information Act and the Health Insurance Portability and Accountability Act of 1996 (HIPAA), including the HIPAA regulations in 45 Code of Federal Regulations parts 160 and 164. We will randomize the patients between 10/1/2020 to 9/5/2023. We will submit all consent forms with the request for data by 9/25/2023. The "CURES Access Period" will be designated from 9/1/2023 to 7/1/2024. We will provide CURES with the first name, last name, DOB, and copy of consent for every participant that we request information. The CA DOJ will be notified upon completion of the study, which is anticipated to be 7/30/2024. Per CURES regulations, the "CURES Data Destruction Date" will be 10/30/2029. On that date the dataset from CURES will be deleted and a notification will be sent to CURES. The CA DOJ will be provided with an advance copy of any manuscript or presentation that uses the CURES data, as well as a copy of final publications. The CA DOJ also will be notified when a team member is added to or removed from the study.

## 8.2 SAFETY AND OTHER PROCEDURES

Safety will be monitored by following up with participants for any adverse events (AE), assessment of adherence, monitoring of biometric information, and questionnaires by support staff.

### Participant safety - Severe Depression & Substance Use Disorders

Study participants will complete the PROMIS Depression questionnaire at baseline and every two weeks throughout the study. Because the surveys are completed electronically, scoring takes place immediately. In a study comparing PROMIS Depression scores with the PHQ-9 commonly used to screen for depression, a t-score greater than 70 indicates severe depression. The REDCap system will be programmed to alert the study team via email if a participant's score is higher than 70. A physician investigator will contact the participant and conduct a clinical assessment of suicide risk, provide education on the importance of a safe treatment plan, direct them to emergency services if indicated, and provide assistance with finding an appropriate treatment provider. If an individual meeting this

threshold can not be contacted by a physician investigator for a phone assessment, the individual will be emailed a list of available resources.

Substance use disorders will be screened using the TAPS 1&2 at baseline and then at week 12. The REDCap system has been calibrated to alert the team when the patient achieves a score >2 on the combined assessment. The research team will then email the patient a list of available resources.

---

### 8.2.1 PROCEDURES

#### Virtual Reality Headset data

Data from the PICO G2 4K device will be aggregated by AppliedVR's cloud-based software solution that implements robust industry standards to maintain secure databases and keep data private. The AppliedVR cloud server is a HIPAA compliant platform. The device account that corresponds with each device will be created using a clinical trial number that is only linked to the patient via our office list of patients enrolled in the study. AppliedVR does not collect personally identifiable information and does not collect IP addresses from synced participant devices in our database. Data will be stored and indexed in the AppliedVR server database whenever devices upload batches of analytic events, and the analytic events are timestamped. The data collected by the device will include time of use, date of use, and the module selected. Our database servers are IP firewalled and whitelisted such that they refuse any connection from IP addresses not preprogrammed by our team.

#### Fitbit data

Data from the Charge 4 device will be aggregated by Fitabase, a fully hosted, cloud-based software solution that implements robust industry standards to maintain secure databases and keep data private. Accordingly, the Charge 4 account that corresponds with each device will be created using an anonymous email address not linked to a real person. Fitabase does not collect personally identifiable information and does not collect IP addresses from synced participant devices. Data will be stored and indexed in the Fitabase SQL Server database in day total, hour, and minute-by-minute intervals. Our database servers are IP firewalled and whitelisted such that they refuse any connection from IP addresses not preprogrammed by our team.

#### Technical Support

Patients in all three arms will receive remote technical support from the research team. The idea is that issuing devices is usually insufficient to achieve behavior change; supporting those devices with high-touch yet scalable care is a vital component.

Patients will be provided with onboarding material as well as emails with a link to our study website. The study website was based on experience from previous remote VR therapy clinical trial and feedback from patients within it. On the website we will have instructional videos as well an extensive FAQ page. The patient will have an onboarding phone call once the device is delivered to their home. During this call, patients will be asked if they reviewed the onboarding video that was linked in the device tracking information email, and coordinators will answer any remaining questions and guide participants through the device or program if necessary. Contact information will be provided for technical support throughout the remainder of the participant's study enrollment.

Redcap survey data will also be monitored. We will assign two technical support staff members to monitor patients in all three arms. Patients will receive a telephone number and email to contact support staff as needed.

VR device metadata will be provided monthly by AppliedVR as CSV files containing timestamped records of content accessed at the individual device level. It will provide the amount of time the patient spent on the device and the modules that they completed.

